10.4.3 ANALYSIS OF THE SECONDARY ENDPOINT(S)

Because this is an unpowered feasibility study, no formal tests of hypothesis will be conducted for the secondary endpoints. All secondary endpoints will be assessed using appropriate descriptive statistics.

10.4.4 SAFETY ANALYSES

Safety will be assessed by summarizing all adverse events, including summaries according to relatedness and seriousness.

10.4.5 BASELINE DESCRIPTIVE STATISTICS

Baseline characteristics and subject demographics will be summarized using appropriate descriptive statistics.

10.4.6 PLANNED INTERIM ANALYSES

10.4.6.1 SAFETY REVIEW

Safety will be assessed on an ongoing basis by the independent Medical Director, Sponsor, and Principal Investigator. No formal interim analyses are planned.

10.4.6.2 EFFICACY REVIEW

Effectiveness will be informally assessed on a periodic basis to ensure an acceptable level of risk for the observed level of efficacy.

10.4.7 ADDITIONAL SUB-GROUP ANALYSES

Due to the small (n=10) sample size, formal sub-group analyses are not possible or planned.

10.4.8 MULTIPLE COMPARISON/MULTIPLICITY

Because no formal tests of hypothesis are planned, the notion of type I error does not exist and controlling for multiple comparisons and multiplicity is not necessary.

10.4.9 TABULATION OF INDIVIDUAL RESPONSE DATA

In addition to tabular descriptive summaries of safety and effectiveness data, line listings of all adverse events and key effectiveness variabiles will provided, by subject.

10.4.10 EXPLORATORY ANALYSES

The ability to perform formal exploratory analyses is limited by the sample size of this trial. All outcome data will be summarized using appropriate descriptive statistics.

10.5 SAMPLE SIZE

This trial is a first-in-human feasibility trial of the Brown Glaucoma Implant. No formal tests of hypothesis are planned, and so sample size is not statistically derived. A total of ten enrolled and implanted subjects are believed to be sufficient to confirm preclinical findings, provide evidence of feasibility of efficacy, and determine whether or not the observed safety profile justifies further study.

10.6 MEASURES TO MINIMIZE BIAS

10.6.1 ENROLLMENT/ RANDOMIZATION/ MASKING PROCEDURES

A study subject will be considered enrolled in the study upon signing Informed Consent. If an enrolled subject does not meet all eligibility criteria, the subject will be subsequently withdrawn from the study. Only enrolled subjects for whom an implant is attempted will be followed and reported on. Since this is a single-arm feasibility study, there will be no randomization or masking/blinding procedures.

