5.6 PARTICIPANT WITHDRAWAL OR TERMINATION

5.6.1 REASONS FOR WITHDRAWAL OR TERMINATION

All subjects enrolled in the clinical study, including those withdrawn from the clinical study, terminated, or lost to follow-up, shall be accounted for and documented. If a subject withdraws from the clinical investigation, the reason(s) shall be reported. Reasons for withdrawal may include, but are not limited to:

- Subject found not to meet eligibility criteria
- Subject did not receive implant
- Subject choice to withdraw consent
- Investigator discretion
- · Lost to follow-up, despite best efforts to locate the subject
 - Three documented attempts to contact the subject, including one certified letter, are required to declare a subject lost to follow up.
- Death (see Section 8.6 for reporting requirements).

If a subject withdraws from the clinical investigation, the reason(s) shall be reported on the End of Study electronic case report form (eCRF) in the EDC system. Data up to the point of withdrawal will be collected. If any SAEs, SADEs or USADEs are open, every effort should be made to follow the subject until resolution. If this is not possible, any open event should be closed or documented as chronic. Normal manufacturer vigilance monitoring of device performance will take place after a subject is withdrawn.

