7.2.5 SCHEDULE OF EVENTS TABLE

Table 3 Schedule of Events

Procedures	Screening/Baseline	Implant	Day 1	Week 1	Week 2	Month 1	Month 2	Month 3	Month 6, 12 & 24	Month 4.5, 8, 10, 15, 18, &21	Unscheduled
Informed Consent	Χ										
Eligibility Verification	Χ										
Medical History (including physical exam)	Х										
BGI Implant		X									
Best Corrected Visual Acuity (ETDRS)	Χ			X	Χ	Χ	Χ	X	Χ		Χ
Applanation Tonometry	Χ		Χ	X	Χ	Χ	Χ	X	Χ	Χ	Χ
Diurnal IOP	Χ								Χ		
Body Temperature	Χ		Χ	X	Χ	Χ	X	X	X		Χ
Central Corneal Thickness	Χ								X		
Slit Lamp Examination	Χ		Χ	X	Χ	Χ	Χ	X	Χ		Χ
Vertical C/D Ratio	Χ								Χ		
Corneal Surface Stain	Χ								Χ		
Indirect Ophthalmic Examination/Dilated Fundus Exam	X				Χ	Χ	X	Χ	X		X
Corneal Endothelial Cell Count	Χ							X	Χ		
Gonioscopy	Χ							X	X		
Optic Nerve Image Analysis	Х								X		
Perimetry of non implanted eye	Х								Х		
Seidel's Test		X	Χ	Χ	Χ	Χ	Χ	Χ	Χ	Χ	Χ
Schirmer Tear Test	Х					Χ		Χ	Х		
Lens Status for Phakic Eyes	Х					Χ		Χ	Χ		
Treatment Satisfaction Questionnaire	Х					Х		Х	Χ		
CIGTS	Χ					Χ		Χ	Χ		
Implant Site Photograph		X	Χ	Χ	Χ	Χ	Χ	Χ	Х	Х	Χ
Screening CRF	Х										
Implant CRF		Х									
Day 1 CRF			Χ								
Week 1 CRF				Χ							
Week 2/Month 2/Unscheduled CRF					Χ		Χ				Х
Month 1/Month 3 CRF						Χ		Χ			
Month 6/Month 12/Month 24 CRF									Χ		

Procedures	Screening/Baseline	Implant	Day 1	Week 1	Week 2	Month 1	Month 2	Month 3	Month 6, 12 & 24	Month 4.5, 8, 10, 15, 18, 821	Unscheduled
Month 4.5, 8, 10, 15, 18, and 21 CRD										X	
Adverse events		X	X	Χ	X	Χ	X	X	Χ	Χ	X
Medication Log	Χ	Χ	Χ	Χ	Χ	Χ	X	X	X	X	X
Device Experience CRF (if applicable)		Χ	Χ	Χ	Χ	Χ	Χ	X	X	X	X
Explantation CRF (if performed)		Χ	Χ	Χ	Χ	Χ	X	X	Χ	X	X
End of Study CRF (when conducted)		Х	Χ	Χ	Χ	Χ	X	X	Χ	X	X

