10.3 ANALYSIS DATASETS

Data from all enrolled subjects for whom an implant is attempted will be included in data analysis. Certain exploratory analyses may be conducted that include only subjects who received an implant, or who have retained an implant for a minimum period of time.

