10.4.2 ANALYSIS OF THE PRIMARY EFFICACY ENDPOINT(S)

The primary endpoint is a binary measure of at least 20% reduction from baseline in diurnal IOP at six months. This endpoint will be descriptively summarized as a proportion of subjects meeting this criterion, along with the corresponding 95% confidence interval.

Given the small sample size of this study, the primary efficacy endpoint will be evaluated several different ways to assess the robustness of study conclusions. One analysis will determine whether or not a subject is classified as success (at least 20% reduction in IOP) based strictly on the baseline and follow-up IOP. Another analysis will be conducted that classifies any subject as a failure if, at the time of the endpoint evaluation, the subject:

- is taking increased glaucoma medication over baseline
- has required glaucoma re-operation
- has experienced a clinically significant post-operative hypotony that results in injury (i.e., no hypotony maculopathy, astigmatism, flat anterior chamber, corneal folds, choroidal effusions, suprachoroidal hemorrhage) or requires invasive intervention
- has been unable to receive an implant
- has discontinued trial participation due to the investigational device
- requires oral or intravenous glaucoma medication
- experienced a serious device-related AE.

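### Protocol 5.6.1 does not limit the no-implant withdrawal reason to unattempted cases, so an incised eye that never held a device may leave a study whose sections 10.3, 10.4.2 and 10.6.1 retain it

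*Protocol*

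**What the plan says.** Four parts of the protocol deal with a subject whose implant was attempted but not completed.

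- **10.3 Analysis Datasets:** "Data from all enrolled subjects for whom an implant is attempted will be included in data analysis". The same section allows exploratory analyses limited to subjects who received an implant, so it treats attempted and received as different things.
- **10.4.2, primary endpoint:** there are two analyses. One classifies success strictly from baseline and follow-up IOP. The other classes a subject as a failure on several grounds, one being that the subject "has been unable to receive an implant".
- **10.6.1:** "Only enrolled subjects for whom an implant is attempted will be followed and reported on".
- **5.6.1, withdrawal:** "Reasons for withdrawal may include, but are not limited to" is followed by a list that contains "Subject did not receive implant". The section continues: "Data up to the point of withdrawal will be collected", and "If any SAEs, SADEs or USADEs are open, every effort should be made to follow the subject until resolution".

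Section 5.6.2 asks for continued follow-up when a device is explanted. Section 7.2.3 times all visits from implant. Section 7.2.4 lists the data taken at early termination, including acuity, tonometry, slit lamp, dilated fundus examination, Seidel's test and adverse events. Section 2.3.1 names an aborted procedure among the known potential risks. SAP section 1 says that data will generally be summarised for implanted subjects.

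**The concern.** The analysis sections assume that an attempted-but-not-implanted subject remains in the study, while the withdrawal section offers wording under which that subject can leave. If a site used it, the eye would have been opened surgically but would have no further scheduled visits. Data not collected cannot be recovered at analysis.

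Three things would be affected:

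- **Safety endpoint.** It is the adverse event rate through six months. Procedure harm that appears after withdrawal, or non-serious harm still evolving at that time, would have no planned visit to detect it.
- **Halting rule in 8.7.** It counts subjects with serious device- or procedure-related events, with thresholds of two among the first five or three in total. At thresholds this low, one late and unobserved event could matter.
- **Strict IOP analysis in 10.4.2.** Section 10.3 includes the subject, but there would be no Month 6 value, and no rule is given for a missing one.

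**Working it through.** The plan has no figure to reproduce. The sample size of ten in 10.5 is not statistically derived, and no alpha, power or failed-attempt rate is stated. The check is mainly a comparison of text.

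**Step 1: does the 5.6.1 item reach a failed attempt?** Section 10.3 separates attempted from received. Section 10.4.2 uses almost the same words as 5.6.1 for a subject in the analysis set, which by 10.3 means an attempt was made. In the protocol's own vocabulary, not receiving an implant therefore includes a failed attempt. Section 5.6.1 does not narrow it.

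**Step 2: does any other provision keep the subject under observation?**

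| Provision | Covers | Does not cover |
|---|---|---|
| 5.6.1, data to withdrawal | Anything recorded by then | Anything later |
| 5.6.1, open serious events | Best-effort follow-up of serious events already open | New events; non-serious events |
| 5.6.2 | An eye from which a device was explanted | An incised eye in which no device was placed |
| 7.2.3 windows | Visits counted from implant | An eye with no implant date |
| 7.2.4 | One examination with adverse events | Harm arising afterwards |
| 10.4.2, second analysis | Counts the subject as a failure; needs no Month 6 IOP | Safety data; the strict IOP analysis |

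Table 3 marks the Explantation form at the Implant visit, so a device placed and removed the same day can be treated as an explant under 5.6.2. The clear gap is the eye in which no device was ever placed.

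**Step 3: how likely is a failed attempt?** The documents give no rate, so f is assumed. For ten attempts, P(at least one) = 1 − (1 − f)^10:

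- f = 2%: 1 − 0.98^10 = 0.183
- f = 5%: 1 − 0.95^10 = 0.401
- f = 10%: 1 − 0.90^10 = 0.651

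Section 10.5 plans ten implanted subjects. The chance of no failure before the tenth success is also (1 − f)^10, so the figures hold on either count. One failed attempt beside ten implants is 1/11, or 9.1% of attempted eyes.

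**Step 4: effect of the SAP population.** Take 7 responders as an illustration only. Among ten implanted subjects the rate is 7/10 = 70.0% (exact 95% CI 34.8 to 93.3). With one failed attempt added as a failure, as 10.3 and the second analysis in 10.4.2 would have it, the rate is 7/11 = 63.6% (30.8 to 89.1). The difference is 6.4 points, well within the interval width.

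**The case against.** The best counter-argument is that the passages can be read together. Section 10.6.1 counts a subject as enrolled at consent, so a category is needed for consented subjects who never reach surgery, and 7.2.1 describes withdrawing unsuitable candidates before surgery is scheduled. The 5.6.1 item fits them. The list is permissive: it gives reasons to record and does not tell a site to withdraw anyone. This stands, and it makes the point an unresolved ambiguity. It does not close the gap, because the benign reading is nowhere stated and most unattempted cases already fall under ineligibility, withdrawn consent or investigator discretion.

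A reader might infer three stronger things that the documents do not support.

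- **That 10.6.1 promises follow-up of every attempted subject and 5.6.1 flatly contradicts it.** The operative word in 10.6.1 is only. The duty to follow is implied, and the word all appears in 10.3, about analysis.
- **That Table 3 authorises withdrawal on the day of an aborted procedure.** The row "End of Study CRF (when conducted") is marked at every column from Implant onward. It allows for termination for any reason.
- **That the surgical harm would go unrecorded and the results would favour the device throughout.** Harm evident by the early-termination examination is captured, and open serious events are followed by best effort. The second primary analysis counts the subject as a failure, and the SAP flow diagram shows premature withdrawals with reasons.

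It is also fair to object that Step 3 gives the chance of a failed attempt, not of a withdrawal. That stands, and the verdict treats the figures accordingly.

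**Conclusion.** The point holds as an unreconciled ambiguity with a narrow but unrecoverable consequence. An eye that was incised but never held a device can, on a literal reading of 5.6.1, leave the study, and no other section sets follow-up for it. The exposure is limited to later or still-evolving non-serious procedure harm, later serious events relevant to the halting rule, and the Month 6 value in the strict IOP analysis. For those items, loss would be tied to surgical difficulty and so would tend to flatter the device.

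The 18%, 40% and 65% figures rest on assumed rates with no anchor in the documents. They are upper bounds on the problem, since a site must also choose to withdraw the subject. The documents do not say whether any attempt failed.

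The SAP adds a separate difficulty. Its general population of implanted subjects omits these subjects from most summaries whatever 5.6.1 says. Its Intent-to-Treat text addresses explanted subjects and not failed attempts. Correcting the withdrawal list alone would not be enough.

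**What to change.** 1. In 5.6.1, limit the withdrawal reason to subjects in whom no implant was attempted, so that it agrees with 10.3, 10.4.2 and 10.6.1. Carry the same wording into the End of Study form instructions.
2. State that attempted-but-not-implanted subjects stay in scheduled data collection and adverse event reporting unless they withdraw consent, and count their visit windows from the date of attempted surgery.
3. Align the SAP population with 10.3 and give attempted-but-not-implanted subjects their own count in the enrolment flow diagram.

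The cost is a few lines of text and study visits for an occasional subject. This concerns study data collection only and proposes no rule for clinical care.

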11 SOURCE DOCUMENTS AND ACCESS TO SOURCE DATA/DOCUMENTS

Investigators are required to maintain on file the accurate, complete, and current records relating to this investigation:

- All correspondence with another Investigator, an IRB or Ethics Committee, MicroOptx, a monitor, or FDA or Competent Authority including required reports
- The signed CIP with any and all amendments
- The approved template of the Subject informed consent form
- Records showing receipt, use, and disposition of all devices, including:
 - Date, quantity, and serial numbers of devices received
 - Names of all persons who received, used or disposed of each device
 - Dates and serial numbers of devices returned to the Sponsor and the reason(s) for return
- IRB or Ethics Committee approval of the CIP and any amendments and renewals
- Competent Authority Approval in those countries where applicable
- The Investigators' agreement and the fee agreement (separate or combined)
- The Report of Prior Investigations and/or the Investigator's Brochure
- The insurance certificate
- Any documentation provided with the device
- Current curriculum vitae for the Principal Investigator and all Sub-Investigators
- Monitoring letters (if applicable)
- Interim/final reports
- Study initiation forms
- Study closure documents

Early BIRD Version 9.0
Protocol 4039 27 JAN2019

In addition to the study administrative documents, Subject records shall be appropriately filed, including the following:

- Signed informed consent forms
- Source documents used for recording data (e.g., device characteristics at implant and followup)
- Records of any adverse event, including supporting documentation
- Records pertaining to Subject deaths during the study
- Relevant source data
- Any other records required by the Sponsor
- Documents showing the dates and reasons for each deviation from the CIP

MicroOptx and designated personnel (e.g. monitors) shall have access to all records listed above, upon request.

12 ETHICS/PROTECTION OF HUMAN SUBJECTS

12.1 INSTITUTIONAL REVIEW BOARD (IRB)

The primary purpose of the IRB is to ensure that the rights and welfare of research subjects are adequately protected. In executing its purpose, the IRB has the authority to approve, require modifications to secure approval, or disapprove this research study. Also, the IRB has authority to suspend or terminate the trial once it is ongoing if it is not being conducted in accordance with the IRB's requirements, or becomes associated with unexpected serious harm to subjects.

Given the early nature and duration of this trial, the IRB will formally review ongoing data (protocol deviations, AEs, and deaths) every six months. Serious Adverse Events will be reported to the IRB according to the IRB's policy.

12.2 ETHICAL STANDARD - STATEMENTS OF COMPLIANCE

This clinical investigation shall be conducted in accordance with the ethical principles that have their origin in the Declaration of Helsinki.

The trial will be carried out in compliance with ISO standard 14155:2011 – Clinical investigation of medical devices for human subjects – Good Clinical Practice

This trial will be listed in clinicaltrials.gov prior to beginning the trial.

This study will not begin until all required approvals and favorable opinions have been obtained from the EC and other governing regulator bodies. All requirements imposed by the EC or other governing bodies will be followed.

12.3 INFORMED CONSENT PROCESS

12.3.1 CONSENT/ASSENT AND OTHER INFORMATIONAL DOCUMENTS PROVIDED TO PARTICIPANTS

Informed Consent is required from all Subjects (or their legal representatives) prior to the Subject's participation in the study.

Other informational materials provided to study participants will include:

- Patient Manual important information for trial participants implanted with the Brown Glaucoma Implant, including contact information for questions and concerns
- Patient Card Medical Alert patient information card

12.3.2 CONSENT PROCEDURES AND DOCUMENTATION

The process of obtaining Informed Consent shall comply with the Declaration of Helsinki, FDA 21CFR 50, ISO 14155-2011 and applicable national regulations (local IRB, Ethics Committee and/or Regulatory bodies, as applicable). The process of obtaining informed consent shall:

- a) Avoid any coercion of or undue influence of Subjects to participate,
- b) Not waive or appear to waive subject's legal rights,
- c) Use native language that is non-technical and understandable to the subject or his/her legal representative,
- d) Provide adequate time for the subject to consider participation and ask questions if necessary,
- e) Informed consent shall always be signed and personally dated by the subject or legal representative and by the Investigator.

The original signed Informed Consent must be retained on file by the Investigator and a copy given to the subject (Investigator's responsibility).

12.4 PARTICIPANT AND DATA CONFIDENTIALITY

Throughout the study, confidentiality shall be maintained at all times, by all parties involved, and all data shall be secured against unauthorized access. Confidentiality of each subject shall be preserved in reports and any publication of the results. Only authorized personnel and their designees will have access to these confidential files. Subject data may be made available to national and foreign regulatory agencies, health or other governmental authorities, under strict confidentiality condition. The investigational sites shall ensure that data (e.g. worksheets, medical records, digital images) forwarded to the Sponsor do not contain any Subject identifying data (such as name and birth date), other than the Subject ID.

It is required that eCRFs be entered in the electronic data entry system provided by the Sponsor. All eCRFs require the Investigator's electronic signature or the Investigator's designee.

Source documents — as per FDA 21CFR 812 and ISO 14155-2011 — are printed, optical or electronic documents including the information in original records and necessary for the reconstruction and evaluation of the clinical investigation. Original source data should remain at the investigational site.

12.4.1 RESEARCH USE OF STORED HUMAN SAMPLES, SPECIMENS OR DATA

A participating Investigator shall provide direct access to source data and documents for Trial-related monitoring, audits, IRB or Ethics Committee review, and regulatory inspection. All subjects' health information will be kept confidential in accordance with all applicable laws and regulations. Subjects' health information may be used to conduct this research, as well as for additional purposes, such as overseeing and improving the performance of products, new medical research and proposals for developing new medical products or procedures, and other business purposes. Information received during the study will not be used to market to subjects; subject names will not be placed on any mailing lists or sold to anyone for marketing purposes.

12.5 FUTURE USE OF STORED SPECIMENS

There will be no human samples or specimens collected and stored for future use in this study.

13 DATA HANDLING AND RECORD KEEPING

13.1 DATA COLLECTION AND MANAGEMENT RESPONSIBILITIES

To ensure data quality and completeness, all required data will be recorded on standardized case report forms (eCRFs) provided by the Sponsor. Case report forms should be completed accurately and completely during and in a timely manner after any treatment in the study. The Principal Investigator or appointed designee must review the case report forms and electronically sign them certifying their accuracy.

MicroOptx follows a data management plan which is on file and available for review. Data will be captured in an electronic data capture system. Data will be reviewed regularly by both study monitors and data associates. Data queries will be issued as needed and require site personnel to make corrections and state the reason for the modification. All entries and modifications will be captured in an electronic system audit trail.

